5.3 Safety Evaluations

Incidence of adverse events from the investigational drug or transfer to ICU

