	o Compliments (c3, c4),
	o Chest X-ray, CT scan
	o COVID-19 PCR
	o Immune phenotype (CD3 T Cell, CD4 T Cell, CD8 T Cell, CD19 B Cell, CD20 B Cell, NK Cell).
OTHER EVALUATIONS	Inflammatory cytokines (IL-1β, IL-1Ra, IL-2, IL-6, IL-10, INF-alpha, INF-gamma, Eotaxin, RANTES & TNF-α).
SAFETY EVALUATIONS	Incidence of adverse events from the investigational drug or transfer to ICU
PLANNED INTERIM ANALYSES	When approximately 50% of patients have completed the study, an interim analysis for safety will be conducted by an independent data monitoring committee. Serious adverse events will be monitored by the research team on an ongoing basis throughout the study.
STATISTICS Primary Analysis Plan	After 10 days of intervention, the Proportion of patients who clinically recovered on day 14 will be compared with control group. Student t test will be used to compare means of both groups.
Rationale for Number of Subjects	To achieve a power of 80% and a two-tailed p-value of <0.05 of an assumed 40% difference between the proportion of patients with clinical cure among the NS group in comparison with the control group, a total of at least 200 patients assigned randomly into the two arms (ie 100 patients per arm) will be needed to be included in the study as calculated using G*Power version 3.1.9.2 (Heinrich-Heine-University Düsseldorf, Düsseldorf, Germany).

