4 STUDY DESIGN

4.1 Study Overview

This is a single center, open-label, controlled, randomized, phase II clinical trial. 200 of subjects are planned. Each subject will be administered a single dose (500 mg) of study drug twice daily for 10 days. Subjects will be assigned to the treatments in random order. Evaluations will be taken daily for evaluationg symptoms imrovpment.

Screening data will be reviewed to determine subject eligibility. Subjects who meet all inclusion criteria and none of the exclusion criteria will be entered into the study.

The following treatment regimens will be used:

- Experimental treatment NS at the following dose 500 mg twice daily
- Comparator Standard care for COVID-19

Total duration of subject participation will be 14 days. Total duration of the study is expected to be 12 months.

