5.2 Secondary Efficacy Endpoints

- Improvement of Clinical Parameters:
- o Time to full clinical recovery
- o Time to progression to pneumonia or hypoxia
- o Duration of illness
- o Discharge to home
- o Normalization of chest radiograph.

o Rate of complications: ICU admission, noninvasive ventilator, superadded infection o Death.

- Normalization of Routine Laboratory Tests:
- o Complete Blood Count (CBC)

o Erythrocyte sedimentation rate (ESR)

o C-reactive protein

o D-dimer

o Liver function test

o Renal function test

o Lactate Dehydrogenase (LDH),

o Immunoglobulins (IgA, IgE, IgG, IgM),

o Compliments (c3, c4),

o Chest X-ray, CT scan

o COVID-19 PCR

o Immune phenotype (CD3 T Cell, CD4 T Cell, CD8 T Cell, CD19 B Cell, CD20 B Cell, NK Cell)

- Additional:

o Inflammatory cytokines (IL-1β, IL-1Ra, IL-2, IL-6, IL-10, INF-alpha, INF-gamma, Eotaxin, RANTES & TNF-α).

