8.3 Formulation of Test and Control Products

SFDA-licensed Marnys CUMINMAR Nigella sativa oil 500mg softgel oral capsules.

No control product will be used.

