8.7 Measures of Treatment Compliance

Subjects will be monitored on daily bases during the study period for their study drug intake and any adverse events.

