9.1.5 Adverse Events

Information regarding occurrence of adverse events will be captured throughout the study. Duration (start and stop dates and times), severity/grade, outcome, treatment and relation to study drug will be recorded on the case report form (CRF).

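### The adverse-event part of the safety endpoint counts only drug-attributed events, and outside the harms listed in 5.2 no all-cause comparison by arm is planned

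*Combined protocol and SAP*

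**What the plan says.** The safety endpoint, in 5.3 and again in the synopsis, is "Incidence of adverse events from the investigational drug or transfer to ICU". It has two parts: adverse events attributed to the drug, and ICU transfer, which has no causality condition.

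The comparison arm is "Comparator Standard care for COVID-19" (4.1), and 8.3 adds "No control product will be used".

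Section 14 names a test for the primary endpoint (14.3) and the secondary endpoints (14.4) and none for safety. The secondary endpoints in 5.2 include some harms without a causality limit: "Rate of complications: ICU admission, noninvasive ventilator, superadded infection", "Time to progression to pneumonia or hypoxia", death, and liver and renal function tests.

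Recording is wider than the endpoint:
- 8.7: "Subjects will be monitored on daily bases during the study period for their study drug intake and any adverse events".
- 9.1.5: "Information regarding occurrence of adverse events will be captured throughout the study", with relation to drug kept as one attribute of each event.
- 10.2: adverse experiences are recorded over the 14 days of monitoring.
- 11.1: the definition of an adverse event needs no causal link.
- 11.2.1: SAEs are documented whether or not related.

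The synopsis also states that at about 50% completion "an interim analysis for safety will be conducted by an independent data monitoring committee". It does not say what that review will tabulate. The research team monitors SAEs throughout.

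**The concern.** All patients have symptomatic COVID-19 at entry (6.2, 6.3), and symptoms of the illness can resemble drug reactions. The trial is open-label, so whoever judges causality knows who took the capsules. The protocol's own scale (11.1, Table 2) makes this harder. The possible category admits events that other factors could readily explain, the unrelated category demands certainty, and nothing lies between them. Section 5.3 does not say which categories count as coming from the drug.

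A count of attributed events in one arm cannot on its own separate background illness from drug effect. The randomised control arm can supply the background rate, but the endpoint as worded does not use it. At stake is the by-arm picture for adverse events outside 5.2, which will mostly be the non-serious ones.

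**Working it through.** **Text check.** Set 5.3 beside 4.1 and 8.3. An event can come from the investigational drug only in someone who took it, so the adverse-event part is 0 in controls treated as planned. Set 5.3 beside 5.2 and section 14. ICU transfer and the 5.2 harms can be counted in both arms, and 14.4 names a test for the latter. All other adverse events have neither an all-cause endpoint nor an analysis in the available text.

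**Inputs.** 100 patients per arm (14.5). The plan states no adverse-event rate or safety power, so there is no figure of its own to reproduce, and every rate below is an assumption.

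**What 5.3 reports.** Let 20% of NS patients have any adverse event, and let a share a of these be attributed to the drug whatever the true cause. The attributed rate on NS is 0.20 × a.
- a = 0.50: 0.20 × 0.50 = 0.10, or 10/100, Wilson 95% CI 5.5% to 17.4%.
- a = 0.25: 0.20 × 0.25 = 0.05, or 5/100, Wilson 95% CI 2.2% to 11.2%.

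The control figure is 0 in each case. None of these results changes with the control arm's own background rate.

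**What an all-cause table reports.** Difference d = p1 − p0, with SE = √[p1(1 − p1)/100 + p0(1 − p0)/100].
- Control 20% (no harm): d = 0; SE = √(0.0016 + 0.0016) = 0.0566; 95% CI −11.1 to 11.1 points.
- Control 10% (10-point excess): d = 0.10; SE = √(0.0016 + 0.0009) = 0.050; 95% CI 0.10 ± 1.96 × 0.050, or 0.2 to 19.8 points.

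The expected differences are 0 and 10 points, given equal ascertainment in the arms.

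**Precision.** For 20% versus 10% at two-sided 5%, the pooled rate is 0.15 and the pooled SE is √(2 × 0.15 × 0.85/100) = 0.0505. Power is Φ[(0.10 − 1.96 × 0.0505)/0.050] = 0.51, or 0.44 with Fisher's exact test. At exactly 20/100 versus 10/100, Fisher's p = 0.073. Under this assumed harm the Wald 95% interval would include zero about 48% of the time.

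**If attribution is informative.** Suppose 80% of true drug events and 20% of background events are attributed (also assumed).
- No harm: 0.20 × 0.20 = 4%.
- 10-point excess over a 10% background: 0.10 × 0.20 + 0.10 × 0.80 = 10%.

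Here 5.3 does respond to harm. With perfect attribution it would be correct.

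**The case against.** The strongest reply is that little safety information is lost. Adverse events and SAEs are recorded regardless of cause, the gravest outcomes are secondary endpoints with a test named, an independent committee reviews safety at the midpoint, and nothing prevents a by-arm table in this exploratory phase II trial. Most of this stands, and it confines the point to the endpoint definition and its planned reporting. It does not remove the point, because nothing in the available text commits the sponsor to that table.

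Some stronger readings are tempting, and the documents do not support them:
- A reader might infer that the whole safety endpoint is zero in controls. It is not; ICU transfer can occur in either arm.
- A reader might infer that no harm is compared by arm. Section 5.2 lists several.
- A reader might infer that control patients' events go unrecorded. Sections 8.7, 9.1.5, 10.2 and 11.2.1 are not restricted to one arm. The wording of 11.1 (administration of a product), 14.1 (dosing) and 15.1 (treatment with the drug) could be read to leave controls out, and needs clarifying.
- A reader might expect a spurious significant excess on NS from testing 5.3 between arms. The plan states no such test.

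Two qualifications also stand. The zero follows from the design: NS is a food spice sold in local pharmacies (section 1) and 7.1 does not bar controls from taking it. And the contents list headings on medical monitoring and a safety management plan that are not in the available body, so the absence of a comparison can be stated only for the text at hand.

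**Conclusion.** The point holds for the adverse-event part of 5.3 and the synopsis. That part is limited to drug-attributed events, is structurally zero in controls treated as planned, and depends on open-label judgement in the NS arm. For adverse events outside 5.2, the available text plans no all-cause comparison by arm.

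Its size cannot be fixed from the documents. If attribution carries no information, 5.3 gives the same result with no harm and with a 10-point excess. If attribution is good, the loss is small. It would be too strong to say that an all-cause table tells the two situations apart: their intervals overlap widely and only the expected differences differ. The gain is an estimate that uses the randomised controls. This is a change that should be made, with medium confidence.

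**What to change.** 1. Redefine 5.3 and the synopsis as the number and percentage of patients with at least one adverse event, and with at least one SAE, regardless of causality, by randomised arm through the 14-day monitoring, with risk difference and 95% CI. SAE collection starts at consent (11.2.1), so list any SAE between consent and randomisation separately.
2. Report ICU transfer separately. Keep drug-attributed events as a descriptive listing for the NS arm.
3. State that 11.1, 14.1 and 15.1 do not leave control patients out of adverse-event recording or the safety table.
4. Tabulate COVID-19 symptoms apart from other adverse events, using one symptom list fixed before analysis and applied to both arms. Note that all patients are symptomatic at entry and that Visit 1 (10.1) lists no symptom record, so new or worsened symptoms are not readily told from existing ones.
5. Use the same by-arm table at the 50% interim safety review.

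The cost is wording in five places (5.3, the synopsis, 11.1, 14.1, 15.1) and one table, from records already provided for. Item 3 should reach the site early: if 11.1 or 15.1 were read as excluding controls, their records could be incomplete. Two limits remain. Ascertainment is still open-label, so an all-cause difference is not guaranteed to be unbiased. Precision is modest (power about 44% to 51% for an assumed 20% versus 10%), so the table should be presented as estimation and not as a confirmatory test.

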6 SUBJECT SELECTION

6.1 Study Population

Subjects with a diagnosis of mild to moderate COVID-19 who meet the inclusion and exclusion criteria will be eligible for participation in this study.

6.2 Inclusion Criteria

-Patients with mild COVID19 (defined as upper respiratory tract infection symptoms in the absence of clinical or radiological signs of pneumonia).

-Adult (18 - 65 years old).

-Written informed consent by the patient (or legally authorized representative) prior to initiation of any study procedures.

-All patients should understand and agree to comply with planned study procedures. -Polymerase chain reaction (PCR)-confirmed infection with Severe Acute Respiratory Syndrome Coronavirus-2 (SARS-CoV-2).

6.3 Exclusion Criteria

-Patients with pneumonia or severe illness requiring admission to intensive care unit. -Asymptomatic patients.

-Severe chronic kidney disease (i.e. estimated glomerular filtration rate [eGFR] < 30 mL/min) or end stage renal disease requiring dialysis

-Severe chronic liver disease (Alanine transaminase [AIT] or Aspartate transaminase [AST] > 5 times the upper limit of normal).

-Pregnancy or breast feeding.

-Anticipated transfer within 72 hours to another hospital that is not a study site.

-Allergy to the study medication.

7 CONCURRENT MEDICATIONS

All subjects should be maintained on the same medications throughout the entire study period, as medically feasible, with no introduction of new chronic therapies.

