SUBJECT SELECTION CRITERIA	 Inclusion Criteria: Patients with mild COVID19 (defined as upper respiratory tract infection symptoms in the absence of clinical or radiological signs of pneumonia). -Adult (18 - 65 years old). Written informed consent by the patient (or legally authorized representative) prior to initiation of any study procedures. -All patients should understand and agree to comply with planned study procedures. Polymerase chain reaction (PCR)-confirmed infection with Severe Acute Respiratory Syndrome Coronavirus-2 (SARS-CoV-2). Exclusion Criteria:
	Patients with pneumonia or severe illness requiring admission to intensive care unit.Asymptomatic patients.

TEST PRODUCT,	 -Severe chronic kidney disease (i.e. estimated glomerular filtration rate [eGFR] < 30 mL/min) or end stage renal disease requiring dialysis -Severe chronic liver disease (Alanine transaminase [AIT] or Aspartate transaminase [AST] > 5 times the upper limit of normal). -Pregnancy or breast feeding. -Anticipated transfer within 72 hours to another hospital that is not a study site. -Allergy to the study medication. SFDA-licensed Marnys CUMINMAR Nigella sativa oil 500mg softgel cansules in oral twice daily dose for 10 days.
OF ADMINISTRATION	
CONTROL PRODUCT, DOSE AND ROUTE OF ADMINISTRATION	NA
DURATION OF SUBJECT PARTICIPATION AND DURATION OF STUDY	Subjects will be on study for up to 14 days Screening: up to 7 days Treatment: 10 days Follow-up: 14 days The total duration of the study is expected to be 12 months
CONCOMMITANT MEDICATIONS	Allowed: Any medication with no interaction with NS Prohibited: ANTICOAGULANT/ANTIPLATELET DRUGS, CNS DEPRESSANTS, CYCLOSPORINE, IMMUNOSUPPRESSANTS
EFFICACY EVALUATIONS	Clinical monitoring for 14 days
PRIMARY ENDPOINT	Proportion of patients who clinically recovered (defined as 3 days of no symptoms) within 14 days after date of onset of symptoms.
SECONDARY ENDPOINTS	 Improvement of Clinical Parameters: o Time to full clinical recovery o Time to progression to pneumonia or hypoxia o Duration of illness o Discharge to home o Normalization of chest radiograph. o Rate of complications: ICU admission, noninvasive ventilator, superadded infection

	o Death.
	- Normalization of Routine Laboratory Tests:
	o Complete Blood Count (CBC)
	o Erythrocyte sedimentation rate (ESR)
	o C-reactive protein
	o D-dimer
	o Liver function test
	o Renal function test
	o Lactate Dehydrogenase (LDH),
	o Immunoglobulins (IgA, IgE, IgG, IgM),

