1 BACKGROUND

The clinical disease termed COVID-19 is caused by a novel betacorona virus, now named SARS-CoV-2. The most common symptoms being reported are fever, cough or chest tightness, and dyspnoea. Most cases are reported to experience a mild illness course (1). Thirty-two per cent required intensive care unit (ICU) admission for respiratory support (1). Laboratory features in this case series commonly included leukopenia, lymphopenia and raised aspartate aminotransferase (1). An epidemiological study of 99 cases of 2019 novel coronavirus pneumonia in Wuhan, China. found an overall mortality rate of 11% with 23% of patients requiring ICU admission (1). Currently, the World Health Organization (WHO) upgraded the status of the COVID-19 outbreak from epidemic to pandemic. In Saudi Arabia, the number of cases of infection with COVID-19 continues to be markedly increasing over the last couple of weeks (2).

Given no specific proven antiviral therapy or vaccination available for COVID-19, the Nigella sativa (NS) seed oil is suggested as a potential supplement due to its known immunostimulant and antiviral activities in previous published studies (3,4). Fortunately, NS oil is available as an oral softgel capsules in commercial pharmacies in Saudi Arabia and licensed by the Saudi Food and Drug Authority (SFDA).

NS (known as Black seed) in Latin language or "Habatulbarakah" in Arabic language, is a well-known food supplement and medicinal plant in the Arabic and Islamic culture. It is used as a food spice and it has plenty of medical claims that originate from different historical backgrounds. The seeds of NS contain several active compounds that have been isolated, identified and reported, most importantly thymoquinone.

In the literature, NS showed several pharmacological activities including antiinflammatory, anti-viral, and immunostimulatory activities (3,4).

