7.1 Allowed Medications and Treatments

Standard therapy for COVID-19 is allowed except for treatments noted in the exclusion criteria described above and as noted in the prohibited medications section below.

Prohibited Medications and Treatments: ANTICOAGULANT/ANTIPLATELET DRUGS, CNS DEPRESSANTS, CYCLOSPORINE, IMMUNOSUPPRESSANTS

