14.5 Sample Size and Randomization

To achieve a power of 80% and a two-tailed p-value of <0.05 of an assumed 40% difference between the proportion of patients with clinical cure among the NS group in comparison with the control group, a total of at least 200 patients assigned randomly into the two arms (ie 100 patients per arm) will be needed to be included in the study as

calculated using G*Power version 3.1.9.2 (Heinrich-Heine-University Düsseldorf, Düsseldorf, Germany).

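### The protocol does not keep control subjects off non-study Nigella sativa, so use of a locally sold remedy could shrink the NS versus no-NS difference.

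*Combined protocol and SAP*

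**What the plan says.** Section 4.1 sets NS 500 mg twice daily against standard care for COVID-19. The trial is open-label, and Section 8.3 states that there is no control product.

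The rules on other treatments are these:

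- **Section 7:** "All subjects should be maintained on the same medications throughout the entire study period". The sentence goes on to limit this to what is medically feasible and to rule out starting new long-term therapies.
- **Synopsis, concomitant medications:** "Allowed: Any medication with no interaction with NS".
- **Section 7.1:** standard COVID-19 therapy is allowed. The prohibited list is "ANTICOAGULANT/ANTIPLATELET DRUGS, CNS DEPRESSANTS, CYCLOSPORINE, IMMUNOSUPPRESSANTS".
- **Section 6.3:** the only exclusion that refers to the study product is allergy to it.

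Section 1 says that "NS oil is available as an oral softgel capsules in commercial pharmacies in Saudi Arabia" and that the plant "is a well-known food supplement and medicinal plant in the Arabic and Islamic culture". Section 2.1 adds that the study brand itself is sold in Saudi community pharmacies.

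Section 9.1.1 records all concomitant medications and therapies at baseline and on study days, and Section 10.2 repeats the review during the 14 days of monitoring. Neither asks about NS by name. Section 14 has no rule for controls who took NS.

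**The concern.** The question is NS versus no NS, so the control arm is informative only to the extent that it is unexposed. Controls know they were not given the product. They have also just been told that it is being tested for their illness, and by the protocol's own account they can buy it locally. A patient already taking black seed oil is eligible and can be randomised to control. A control who starts a short course after randomisation is not clearly starting a long-term therapy, so the restriction in Section 7 does not plainly cover that case.

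Exposure in the control arm pulls the two recovery proportions together. The bias is toward no difference, and a null result could not separate an inactive product from a comparator that also received it.

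**Working it through.** **Inputs from the documents.** 100 per arm, 1:1, two-sided 5%, 80% power (Section 14.5: "To achieve a power of 80% and a two-tailed p-value of <0.05"). The effect is "an assumed 40% difference between the proportion of patients with clinical cure among the NS group in comparison with the control group". The text does not say whether this is absolute or relative, and it gives no control rate.

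**Inputs assumed.** c, the share of controls taking non-study NS, is not in the documents; 10%, 20% and 30% are shown, with 50% as an extreme. Non-study NS is taken to work as well as the study capsules.

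**Step 1: reproduce N = 200.**

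- Two-sample t test with standardised effect d = 0.40. The normal approximation is n = 2(1.960 + 0.842)²/0.40² = 98.1 per arm. The exact noncentral-t calculation gives 99.08, so 100 per arm and 200 in total, with power 80.4%.
- Absolute 40-point difference in proportions. This needs 18 to 24 per arm for control rates from 5% to 55% (36 to 48 in total), so it does not reproduce 200.
- Relative 40% increase. This gives about 100 per arm only at an unstated control rate near 48–49% (103 and 98 per arm), or near 50% with continuity correction (103 per arm).

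The d = 0.40 reading is therefore used as the main case, because it needs no assumed control rate.

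**Step 2: dilution.** Let p₀ be the recovery proportion without NS and p₁ with NS. The control arm then shows p₀ + c(p₁ − p₀), and the difference between arms is (1 − c)(p₁ − p₀). On the standardised scale the effect becomes 0.40(1 − c).

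Existing users in the NS arm do not offset this. If extra NS adds nothing for them, and both arms contain the same share of users, the difference is still (1 − c)(p₁ − p₀).

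**Step 3: power at 100 per arm, d = 0.40 (noncentral t).**

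| c | Diluted d | Power | n per arm to regain 80% |
|---|---|---|---|
| 0 | 0.40 | 80.4% | 100 |
| 10% | 0.36 | 71.7% | 123 |
| 20% | 0.32 | 61.5% | 155 |
| 30% | 0.28 | 50.4% | 202 |
| 50% | 0.20 | 29.1% | 394 |

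Hand check at c = 20%: 0.32 × √(100/2) = 2.263; 2.263 − 1.960 = 0.303; Φ(0.303) ≈ 0.62.

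**Step 4: the other two readings.** For two proportions, power = Φ[(Δ − 1.96√(2p̄(1 − p̄)/n)) / √((p_c(1 − p_c) + p_t(1 − p_t))/n)], where p_c and p_t are the control and NS proportions, p̄ is their mean and Δ = p_t − p_c.

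- **Absolute 40 points, assumed 30% vs 70%.** At c = 30% the control arm shows 30% + 0.3 × 40 = 42%, so Δ = 28 points. Power = Φ[(0.28 − 1.96 × 0.0702)/0.0673] = Φ(2.11) ≈ 98.3%. At c = 50%, Δ = 20 points and power is 82.8%.
- **Relative 40%, assumed 50% vs 70%.** Δ falls from 20 to 18, 16 and 14 points at c = 10%, 20% and 30%. Power falls from 82.8% to 74.6%, 64.7% and 53.6%.

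**The case against.** The strongest reply is that the protocol is silent on non-study NS rather than permissive. That is correct, and it rules out several stronger readings that a reader might infer.

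- **That the plan expressly allows NS in controls.** No sentence does. The synopsis wording is most naturally about drugs taken alongside NS, and Section 7.1 speaks of standard COVID-19 therapy. Any permission is by omission.
- **That controls already using NS are told to continue.** This follows from Section 7 only if a supplement counts as a medication. Section 1 calls NS a food supplement, medicinal plant and spice, and Section 7 is qualified by medical feasibility.
- **That Section 13 would not treat NS use as a violation.** Its list is expressly not exhaustive. What can be said is that the protocol sets no NS requirement for anyone to breach.
- **That extra NS in the treated arm makes the result uninterpretable.** The randomised contrast remains valid as the study regimen added to background use, though diluted.
- **That a serious loss of power is established.** It depends on an undocumented c and on the reading of the 40% difference. Under an absolute 40-point effect, power hardly suffers. Weaker products, or use as a spice, would dilute less than (1 − c).

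It is also fair that general recording of concomitant therapies may reveal some use, that the bias is toward no difference, and that the trial is an exploratory phase II study. None of this closes the gap. Recording after the fact does not prevent exposure, and the primary objective is clinical efficacy, so an unexposed comparator matters.

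**Conclusion.** The concern holds as a gap in the design: nothing in the eligibility criteria, the prohibited list or the maintenance rule keeps open-label controls off a product that the protocol itself describes as familiar and locally on sale. The consequence is attenuation of the primary contrast, by a factor of (1 − c) if non-study NS is fully effective and by less if it is not.

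The shrinkage of the estimate appears on every reading of the planned effect. The power loss does not: it is substantial if the design effect is d = 0.40 or a relative 40% near a 50% control rate, and small if it is an absolute 40 points. The omission is certain from the text; its size is not, because the documents give no rate of NS use. This should be fixed, but it does not invalidate the trial.

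**What to change.** 1. In Section 7.1 and the synopsis, add non-study NS oil, capsules and medicinal preparations to the products not permitted, for both arms, from consent to the end of monitoring.
2. State this as an exception to the Section 7 maintenance sentence, so that the two do not conflict.
3. Ask about NS by name when concomitant medications are recorded at Visit 1 (10.1) and in the daily review (10.2).
4. In Section 14, keep exposed controls in their randomised arm and report how many there were.

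Excluding current users at entry (6.3) is an option rather than a necessity. If recent use is also excluded, the sponsor must define the window.

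The cost is a short amendment and one added question in reviews already planned. Existing users would have to stop or would not enter. The recruitment cost cannot be sized from the documents and would grow with how common NS use is.
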